### 12.0 Timeline

	Jan-Jun 2015	Jul-Dec 2015	Jan-Jun 2016	Jul-Dec 2016	Jan-Jun 2017	Jul-Dec 2017	Jan-Jun 2018	Jul-Dec 2018
Community mobilisation in Durban informal settlements								

Gain ethics approval and access for the study	■							
Develop questionnaire and evaluation materials, gain ethics approval	■							
Intervention delivery (Stepping Stones/ Creating Futures)	■	■						
Baseline measures	■	■						
12 month follow up			■	■				
24 month follow up					■	■		
Data analysis							■	■
Writing							■	■
Dissemination including finalising and publishing curriculum								■

### 13.0 Funding

The research is funded by the United Kingdom Government's Department for International development (DFID).

The total project for the budget is £800,000. The summary of the budget is provided here.

	2015	2016	2017	2018
Intervention	£150,000			
Fieldwork R1	£80,000			
Fieldwork R2		£120,000		
Fieldwork R3			£150,000	
Data analysis			£50,000	£50,000
Control Intervention				£200,000

## **16.0 Appendices**

Please find separately attached:

- Appendix 1: Male Baseline Quantitative Questionnaire
- Appendix 2: Female Baseline Quantitative Questionnaire
- Appendix 3: Male 12 and 24 month Quantitative Questionnaire
- Appendix 4: Female 12 and 24 Month Quantitative Questionnaire
- Appendix 5: Confidentiality Agreement
- Appendix 6: Information Sheet and Informed Consent
- Appendix 7: Gatekeeper Letter

Cluster Randomized Control Trial of the Stepping Stones and Creating Futures Intervention to Prevent Intimate Partner Violence amongst Young People in South Africa: Statistical Analysis Plan

[name], [name] & [name]

18 September 2018

1. Background

Intimate partner violence (IPV) is a global public health problem. Globally, a third of women are likely to experience IPV in their lifetime and experience of IPV is associated with worse health for women. IPV is exceedingly high in informal settlements in South Africa driven by high levels of poverty, gender inequalities, poor mental health, and substance use. The Stepping Stones and Creating Futures intervention was developed to reduce women's experiences, and men's perpetration of IPV in urban informal settlements in South Africa, through transforming gender norms, and strengthening livelihoods. The study protocol was published in *BMC Public Health* in 2017 and included a short overview of statistical methods. This statistical plan was developed from November 2017 and finalized on 28 September 2018, before database lock.

2. Methods and design

2.1. Study overview

The Stepping Stones and Creating Futures intervention trial is a cluster randomized control trial (CRT), with two arms and is open label. The study population are out-of-school young women and men aged 18-30 (at baseline), resident in informal settlements, and without formal employment. 34 clusters were identified, using both naturally-occurring clusters and researcher-imposed clusters, and then randomized 1:1 by a statistician, blinded to cluster names using numbers.

Because of practical reasons, 16 control clusters had data collected September 2015-December 2015, while 1 control cluster had data collected in August 2016. Phase 1 intervention clusters had data collected January 2016-February 2016, with the intervention delivered until June 2016. Phase 2 intervention clusters had data collected August 2016 – September 2016, with the intervention delivered from then - February 2017. In total 680 women and 677 men were recruited into the study. The study protocol provides further detail on study rationale, randomization, data collection and sample size calculation.

2.2. Intervention

The Stepping Stones and Creating Futures is a participatory intervention, which primarily works with single sex groups. Groups of approximately 20 in size. The intervention seeks to transform gender norms and strengthen livelihoods. It is delivered by same-sex, trained facilitators, and comprises of 21 sessions, each approximately 3 hours long.

2.3. Flow of clusters and participants

The flow of clusters and participants through the trial will be reported using the CONSORT extension for cluster randomized control trials [Figure 1]. The flow diagram will include the number of clusters and cluster randomization, recruitment at baseline by arm, and number of participants at each time point. It will also outline the number of participants withdrawing from the trial at each time point.

[figure not shown]

Figure 1: Cluster and participant timeline

2.4. Data collection and management

Randomization was at the cluster level. Once clusters had been recruited, the study statistician randomized clusters using the Microsoft Excel function to randomly allocate equal number of clusters to the intervention and control arm. The statistician was blinded to cluster names. Randomization occurred before recruitment of participants because of political sensitivities.

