### **7.6 Randomisation and blinding to study arm**

Randomisation will be undertaken by cluster after clusters have agreed to participate in the study. Community gate keepers will provide permission to work in a cluster/informal settlement (see 9.1 below). Clusters thereafter will not be blind to their study arm.

All clusters will be allocated numbers and the randomisation will be performed by [name], MRC biostatistician, using a system of numbers. At the time of randomisation she will not know which number is allocated to which cluster. We are not doing public randomisation because of political sensitivities and that clusters are within wards, rather than wards themselves.

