## **9.2 Recruitment of participants**

Once permission to access communities has been granted and clusters have been identified and randomised Project Empower will host a number of open community meetings where they will brief community members about the trial, its nature and design. Community meetings are relatively regular in informal settlements and as such are well known. Also, flyers with adequate information about the trial and project contact details will be handed out during the community meetings. During these community meetings, Project Empower will request those eligible and interested in the trial to contact the project staff by sending free 'please call me' messages from cell phones. The majority of young people in informal settlements have access to cell phones. Those who do not can easily access cell phones through vendors at the side of the road who offer low-calls for people. In addition, 'please call me' messages are free to send, as such young people are likely to be able to borrow cell phones to make initial contact.

In addition, Project Empower will hire two young people from the local community to support recruitment. In clusters where there will be an intervention, these two will become facilitators delivering the intervention. These young people will also support recruitment in the communities and hand out flyers to potential participants encouraging contacting of Project Empower.

Those who made contact with the project staff will then be invited to meet with the project staff in a central location in their community. These spaces will vary depending on communities – but could include a community hall, a spare room off a shop, or sports field. There will be a two day window where Project Empower and HEARD staff will be at this location. Upon arriving potential participants will have further details about the trial will be explained to them, after which they will be invited to participate in the trial (e.g. what it entails, length of study etc.). Informed consent process will only occur after initial agreement of participants.

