3.3. Unadjusted and adjusted analysis

All comparative analyses will allow for the clustered nature of the data to ensure correct confidence intervals and type I error rates are calculated. As the trial includes at least 34 clusters, the analyses will be based on the individual-level summarized data. For each outcome, unless otherwise specified, the primary analysis will be the covariate-adjusted analysis, with the statistical models including the stratification variables and baseline values for the outcome under consideration, where available.

Adjustment for baseline covariates is often advised firstly to correct for any chance imbalances in important baseline variables following randomization, and secondly, because adjusting for highly important baseline variables in an RCT can improve the precision of treatment effect estimates even when the outcome measure is binary. Statistical testing for baseline imbalances is not advised and instead key covariates should be selected prior to analysis based on the likely magnitude of the association with the

outcome measure (European Agency for the Evaluation of Medicinal Products, 2003). We have, however, looked at whether there were meaningful differences at baseline by looking at standardized mean differences. We will also perform a multivariable logistic regression to consider any imbalance that may occur in important baseline characteristics known to predict IPV outcomes between the groups using the following variables:

- Baseline term for variable
- Controlling behaviors
- Food insecurity
- Any earnings in past month (none or R1 or more)
- Childhood trauma
- Age
- Education
- Alcohol use

This selection of variables is based on baseline analysis of the data predicting past year physical and/or sexual IPV. Time will also need to be adjusted for since intervention and control clusters were not measured concurrently.

Odds ratios will be quoted together with their 95% confidence intervals and exact P-values. Generalized estimating equations will be used to account for the clustered-nature of the data in the primary analysis (**Section 3.5.1**).

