3.5.2. Analysis of secondary outcomes

Secondary outcomes will be compared between groups based on the complete data only. Data will be analyzed on an individual-level.

Table 2 provides the proposed analyses for each of the primary and secondary trial outcomes. These analyses will be adjusted for the baseline term of the variable, education and food insecurity.

Table 2: Analysis Methods for trial outcomes

Intention to treat analysis: Primary outcomes			
	Measure	Method of scaling	Proposed analysis
Physical IPV at 24 months	WHO	Binary (never vs once or more)	GEE, odds ratios
Sexual IPV at 24 months	WHO	Binary (never vs once or more)	GEE, odds ratios
Severe IPV at 24 months	WHO	Binary (never or once vs more than once)	GEE, odds ratios
Controlling behaviours at 24 months	Modified SRPS	Mean	Mixed effects linear regression, mean difference
Earnings in the past month at 24 months		Mean	Mixed effects linear regression, mean difference
Intention to treat analysis: Secondary outcomes			
	Measure	Type of variable	Proposed analysis
Gender attitudes at 24 months	Modified GEMS	Mean	Mixed effects linear regression, mean difference
Depressive symptomology at 24 months	CESD	Mean	Mixed effects linear regression, mean difference
Suicidal ideation at 24 months		Binary	GEE, odds ratios
Life circumstances at 24 months		Mean	Mixed effects linear regression, mean difference
Problem alcohol use at 24 months	AUDIT	Mean and binary (cut-off at 7/8)	Mixed effects linear regression, mean difference And GEE, odds ratios
Quarreling about alcohol at 24 months		Binary	GEE, odds ratios
Last sexual partner at 24 months		Binary (main vs other partners)	GEE, odds ratios
Transactional sex at 24 months		Binary (never vs once or more)	GEE, odds ratios
Work shame at 24 months		Mean	Mixed effects linear regression, mean difference
Work stress at 24 months		Mean	Mixed effects linear regression, mean difference

Stealing because of hunger at 24 months		Binary (never stolen vs once or more)	GEE, odds ratios
Mobilization at cash in emergencies at 24 months		Binary (very difficult/somewhat difficult vs fairly easy/easy)	GEE, odds ratios

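### Recruitment followed open allocation and the SAP does not fix one covariate set for the primary models, so measured recruitment differences can enter the primary IPV estimates

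*SAP*

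**What the plan says.** **Order of events.** SAP 2.4: "Randomization occurred before recruitment of participants because of political sensitivities". Protocol 9.2 gives the same order: once "clusters have been identified and randomised Project Empower will host a number of open community meetings". Protocol 7.6 adds: "Clusters thereafter will not be blind to their study arm". SAP 2.1 calls the trial open label.

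**Who recruited, and what was offered.** SAP 2.4.1 describes community mobilisation and snowball sampling by the implementing organisation together with external fieldworkers. Protocol 9.2: "Project Empower will hire two young people from the local community to support recruitment". It continues: "In clusters where there will be an intervention, these two will become facilitators delivering the intervention". Under Protocol 7.2 and 9.9, control participants receive R300 at baseline and the intervention only after follow-up. Intervention participants receive R100 and are offered the workshops from the start.

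**Adjustment.** SAP 3.3 opens its rationale with: "Adjustment for baseline covariates is often advised firstly to correct for any chance imbalances in important baseline variables following randomization". It defines the primary adjusted model by stratification variables and the baseline value of the outcome. It then announces a further multivariable logistic regression with eight variables, explaining: "This selection of variables is based on baseline analysis of the data predicting past year physical and/or sexual IPV". It adds that time needs adjustment because the arms were not measured concurrently. SAP 3.5.1, on the primary outcomes, names no covariates. SAP 3.5.2 introduces Table 2, which covers primary and secondary outcomes, and says: "These analyses will be adjusted for the baseline term of the variable, education and food insecurity".

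**The concern.** Randomising clusters makes the clusters comparable in expectation. It does not make the enrolled individuals comparable when enrolment happens with the arm known, through people whose later role differs by arm, and with a different offer in each arm. Any resulting difference in IPV risk is not chance imbalance, and randomisation does not average it away.

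With recruitment complete, the remaining protection is adjustment for measured predictors. The SAP has identified such predictors but does not say clearly which of them are in the primary models. Two things are at stake. Measured differences in predictors left out of the model can appear as a treatment effect. And because several models can each be called primary, the choice between them could be made after the results are seen.

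**Working it through.** The plan gives no figure for baseline imbalance or its effect, so there is none to reproduce. The first two steps compare passages; the rest are illustrations under stated assumptions.

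**Step 1. The covariate sets side by side.**

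| Place | Terms besides arm |
|---|---|
| SAP 3.5.1 | none named |
| SAP 3.5.2 | baseline value, education, food insecurity |
| SAP 3.3, primary adjusted model | stratification variables, baseline value |
| SAP 3.3, list | baseline value, controlling behaviours, food insecurity, any earnings, childhood trauma, age, education, alcohol use |
| SAP 3.3, after the list | time |
| Protocol 10.2 | age, cluster, baseline IPV prevalence |

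All three terms of 3.5.2 are in the eight-term list, so 8 − 3 = 5 are missing: controlling behaviours, any earnings, childhood trauma, age and alcohol use. Time is missing as well. Protocol 7.6 and SAP 2.1 and 2.4 describe 1:1 randomisation without strata, so the stratification variables refer to nothing in these documents.

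**Step 2. Time.** SAP 2.1 dates baseline to September–December 2015 for 16 of 17 control clusters. Intervention baselines fall in January–February 2016 and August–September 2016. Those 16 control clusters therefore precede every intervention cluster, and one control cluster (August 2016) shares a period with intervention clusters. Time is nearly confounded with arm, so whether and how it enters can change the estimate and its precision.

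**Step 3. How far one omitted factor could move the estimate.** Assume a binary predictor with prevalence q0 = 40% in one arm and q1 = 45–60% in the other, and risk ratio R = 1.25–2.0 for IPV. The arm risk ratio is multiplied by [1 + q1(R − 1)] / [1 + q0(R − 1)].

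- Mild corner: (1 + 0.45 × 0.25) / (1 + 0.40 × 0.25) = 1.1125 / 1.10 = 1.01.
- Extreme corner: (1 + 0.60) / (1 + 0.40) = 1.14.
- In the other direction: 0.99 to 0.88.

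For comparison, the first row of the table in Protocol 7.7.1 implies 29/36 = 0.81.

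**Step 4. What adjustment can and cannot remove.** A small simulation used 34 clusters of 14, no true effect, exchangeable GEE and 300 runs per scenario. Recruitment shifted one predictor by 0.25 SD between arms (assumed). The smaller model had the baseline outcome only, not the full three-term set.

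| Shift in | OR, baseline outcome only | OR, plus listed covariates |
|---|---|---|
| listed covariates | 0.91 | 1.01 |
| an unmeasured factor | 0.91 | 0.90 |
| both | 0.82 | 0.90 |

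The fuller set removes the measured part and leaves the unmeasured part. Rejection rates were already 0.07–0.08 with no shift. They stayed at 0.07–0.08 with the measured shift alone, and fell from 0.17 to 0.08 when both shifts were present and the list was added.

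**Step 5. Illustrative error rate.** Inputs: 17 clusters per arm (Protocol 7.7); 14 followed up per cluster, k = 0.2 and pilot prevalence 41–45% (Protocol 7.7.1); two-sided 5% (SAP 3.2).

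SE = √{[2p(1 − p)/14 + 0.04 × 2p²]/17}

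- p = 0.41: √[(0.03456 + 0.01345)/17] = 0.053
- p = 0.45: √[(0.03536 + 0.01620)/17] = 0.055

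With residual shift b, the error rate is P(Z > 1.96 − b/SE) + P(Z < −1.96 − b/SE).

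| Assumed b | Error rate |
|---|---|
| 3 points | 0.085–0.087 |
| 4 points | 0.112–0.117 |
| 6 points | 0.193–0.204 |

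The planned differences at these prevalences are 41 − 33 = 8 and 45 − 36 = 9 points. The cluster counts in that table are not used here. The standard formula for proportions does not reproduce them (it gives 55.15, so 56 per arm, for 41% versus 33%, against 16 stated). That is a separate matter.

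**The case against.** **The three-term set may not be the primary set.** It stands under the secondary-outcomes heading, and 3.3 defines the primary model differently. Conversely, 3.3 gives its definition as a default that yields to anything specified elsewhere, so 3.5.2 may override it. Both readings are fair. A reader might infer that the primary models adjust for three variables only; the documents support no more than that the set is not uniquely defined.

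**The eight-variable list may be an additional analysis.** The SAP introduces it as something also to be done, so it need not contradict 3.5.2. This stands. The firm conflicts are the time term and the stratification variables. On this reading, though, five predictors that the SAP itself treats as important stay outside the primary model.

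**Bias is not shown.** No imbalance values are given. Standardised differences were examined, although not reported. The baseline value of the outcome is in both 3.3 and 3.5.2 and absorbs part of any difference. Protocol 9.1 has the project presented without emphasis on violence or livelihoods, which makes selection on IPV risk less direct. Local recruiters were hired without restriction to one arm, and study staff explained the trial and invited participants (Protocol 9.2). All of this stands and limits the point to a risk.

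**The assumed shifts may be too large.** An OR of 0.91 at 41–45% prevalence is about 2.3 points, which gives an error rate near 7%. A 6-point shift needs roughly the extreme corner of Step 3 (0.41 × 0.14 = 0.057; 0.45 × 0.14 = 0.063). Also, 41–45% is the prevalence of physical and/or sexual IPV combined, whereas the SAP's primary outcomes are physical, sexual and severe IPV. This stands, so the error rates are illustration only.

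**Conclusion.** The point holds as a specification gap combined with a design risk. Recruitment after open allocation, arm-linked recruiters and different offers are documented, so describing imbalance only as chance does not fit this design. The SAP does not say which covariates are in the primary models. On the 3.5.2 set, five listed IPV predictors and time are left out, and measured differences in them can enter the primary IPV estimates.

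A reader might go further and conclude that recruitment bias has entered the result, or that the full list would remove it. The documents support neither: they report no imbalance, and adjustment does not reach unmeasured selection. The direction and true size of any bias cannot be obtained from them. The figures of about 9% (3 points) and 19–20% (6 points) rest on an assumed residual shift, not divided into measured and unmeasured parts, and on the planning values for cluster size, k and prevalence.

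**What to change.** - **SAP 3.5.1, IPV outcomes.** State one set for physical, sexual and severe IPV, taken from the 3.3 list: baseline value, controlling behaviours, food insecurity, any earnings, childhood trauma, age, education and alcohol use. Keep the three-variable model of 3.5.2 as a named sensitivity analysis.
- **Controlling behaviours and earnings.** Name their sets separately. The 3.3 list was chosen to predict IPV. It would duplicate the baseline term for controlling behaviours and largely overlap it for earnings. For the same reason, do not extend it to every secondary outcome.
- **Time.** In the same place, say how the time term of 3.3 is defined and whether it is in the primary model, and note that it is nearly confounded with arm.
- **Stratification variables.** Define them or delete the phrase.
- **SAP 3.3.** Say that recruitment followed allocation, so imbalance may be systematic. Report the standardised differences by arm and sex. State unmeasured selection as a limitation.

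The cost is SAP wording. The listed variables come from the baseline data, so no new collection is needed. The downside is a few more parameters in models with about 17 × 14 = 238 people per arm per sex.

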2.4.1. Data collection

Data was collected by trained fieldworkers. Project Empower (the implementing NGO), in conjunction with external fieldworkers, went to communities and used a community mobilization process to identify potential participants. Over two to three days, through community engagement and snow-ball sampling, the target of 20 women and 20 men were recruited per cluster.

2.4.2. Integrity of data

Data was through self-completed questionnaires on cellphones, in either English, Zulu or Xhosa. The questionnaire had in-built skip patterns and logic checks. Data automatically uploaded to a server and was

downloaded regularly. At 24 months, audio (ACASI) was used to improve understanding by participants. Range and logic checks will be performed on data before analysis.

2.5. Outcomes

2.5.1. Primary outcomes

- Four primary outcomes are linked to IPV:
 - Any past year physical IPV perpetration (men), and experience (women). This is assessed using a modified WHO VAW scale that has been adapted and widely used in South Africa. Five questions are asked about physical IPV perpetration (men) and experience (women) in the past 12 months. Past year physical IPV is coded as positive (1) for anyone responding positively to one or more items on the scale;
 - Any past year sexual IPV perpetration (men), and experience (women) uses the same approach as for physical IPV. Three sexual IPV questions are asked about experiences in the past 12 months. Past year sexual IPV is coded as positive (1) for anyone responding positively to one or more items on the scale;
 - To assess severe past year sexual and/or physical IPV perpetration (men) and experience (women), physical and sexual IPV scales are combined to be a total of eight items. Past year severe sexual and/or physical IPV is assessed as positive if a person responds to two (or more) items once, or one item as few (or more), essentially creating a more than once categorization.
 - Controlling behaviours are assessed using a modified Sexual Relationship Power (SRP) scale [43] with 8 items. Higher scores refer to more controlling behaviours;
- One primary outcome reflects the objective of the Creating Futures component of the intervention, around strengthening livelihoods:
 - Past month earnings are used to assess overall income and livelihoods. A single item question asks, “Considering all the money you earned from jobs or selling things (excluding grants), how much did you earn last month?” Responses are in South African Rands (ZAR) and a continuous scale.

